11.2.3. Adverse Events of Special Interest

Adverse events of Special Interest include events that Janssen Research & Development is actively monitoring as a result of previously identified signals detailed in the SYLVANT prescribing information. These adverse events are:

- Infections
- Hepatotoxicity
- Gastrointestinal Perforations
- Hemoglobin increases, including polycythemia

11.2.4. Serious Adverse Event (SAE)

A serious adverse event (SAE) or reaction is defined as "any adverse event occurring at any dose that suggests a significant hazard, contraindication, side effect, or precaution." An adverse event or suspected adverse reaction is considered "serious" if, in the view of the sponsor investigator, it results in any of the following outcomes:

• Death. A death that occurs during the study or that comes to the attention of the investigator during the protocol-defined follow-up after the completion of therapy must be reported whether it is considered to be treatment related or not;

- A life-threatening adverse event. A life-threatening event is any adverse therapy experience that, in the view of the investigator, places the participant at immediate risk of death from the reaction as it occurred;
- Inpatient hospitalization or prolongation of existing hospitalization with the exception of hospitalization relating to glycemic control in type 1 diabetes;
- Persistent or significant incapacity or substantial disruption of the ability to conduct normal life functions;
- Congenital anomaly or birth defect;
- Important medical events* that may not result in death, be life-threatening, or require hospitalization may be considered serious when, based upon appropriate medical judgment, they may jeopardize the patient or subject and may require medical or surgical intervention to prevent one of the outcomes listed above;
- Is a suspected transmission of any infectious agent via a medicinal product

*Medical and scientific judgment should be exercised in deciding whether expedited reporting is also appropriate in other situations, such as important medical events that may not be immediately life threatening or result in death or hospitalization but may jeopardize the subject or may require intervention to prevent one of the other outcomes listed in the definition above. These should usually be considered serious.

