4.4. Safety Objective

Evaluate adverse effects associated with single-dose infusion of Siltuximab in subjects with T1D.

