9. STUDY TREATMENT

Siltuximab (SYLVANT™) is an interleukin-6 (IL-6) monoclonal antibody antagonist indicated for the treatment of patients with multicentric Castleman's disease (MCD) who are human immunodeficiency virus (HIV) negative and human herpesvirus-8 (HHV-8) negative. Siltuximab has not be studied in patients with Type 1 diabetes.

9.1.Test Formulation

Siltuximab is provided in single-use vials containing 100 or 400 mg of lyophilized powder. The product is administered as an 11 mg/kg dose given over approximately 1 hour by intravenous infusion.

Instructions for preparation and administration of the drug is reviewed in Section 10.4. Complete dosing instructions are provided in the SYLVANT prescribing information (Attachment 2).

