10.1.3. Metabolic Assessments

- 2-hour mixed meal tolerance test;
- HbA1c;
- Insulin use and home blood glucose measurements.

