11.3. Safety assessments and Collection of Safety Data

This is an exploratory study designed to assess the effects of a single dose of Siltuximab on a select set of immune parameters. All adverse events, regardless of causality, special reporting situations, and product quality complaints will be collected from the time a subject has signed and dated an Informed Consent Form (ICF) until completion of the subject's last study-related procedure (which may include contact for follow-up safety).

The Investigator(s) will treat participants with adverse events appropriately and observe them at suitable intervals until the events resolve or stabilize. Adverse events may be discovered through:

- observation of the participant;
- questioning the participant;
- unsolicited complaints by the participant.

All serious adverse events, adverse events of special interest, product quality complaints, and special situations including pregnancies, whether serious or non-serious, related or not related, following exposure to Siltuximab will be documented by the Sponsor Investigator (or sub-Investigators) and recorded in subject's source documents. Events will be assessed and reported consistent with the ICH Guideline for Good Clinical Practice, 21 CFR 312.32 for expedited safety reporting, per the guidance of the DHHS Office for Human Research Protections (OHRP), and according to any reporting requirements outlined in this protocol.

Confidential Page 18 of 28

Adverse events with the exception of hypoglycemia or hyperglycemia will be graded per the National Cancer Institute's Common Terminology Criteria for Adverse Events Version 4.03 (published May 28, 2009). An adverse hypoglycemic event is defined as one resulting in loss of consciousness, seizure, or requiring assistance of others due to altered state of consciousness. An adverse hyperglycemic event is one resulting in diabetic ketoacidosis (DKA).

Duration (start and stop dates and times), severity/grade, outcome, treatment and relationship to study drug (not, unlikely, possibly, probably, or definitely related) will be recorded on source documents. The batch and lot number of the product will be recorded for all patients, including dose and date of infusion.

11.3.1.SAEs and Special Reporting Situations

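### The SAE exception for glycemic admissions also covers unplanned ones, so a post-infusion DKA admission can be under-classified; insulin use and home glucose are listed but never scheduled

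*Combined protocol and SAP*

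**What the plan says.** - **Safety objective (4.4):** "Evaluate adverse effects associated with single-dose infusion of Siltuximab in subjects with T1D". Section 9 adds: "Siltuximab has not be studied in patients with Type 1 diabetes".
- **SAE definition (11.2.4), hospitalization criterion:** an inpatient stay, or the lengthening of one, is serious "with the exception of hospitalization relating to glycemic control in type 1 diabetes". The other criteria (death, life-threatening, incapacity, congenital anomaly, important medical event, suspected transmission of infection) carry no glycemic exception.
- **Grading (11.3):** "Adverse events with the exception of hypoglycemia or hyperglycemia will be graded" under CTCAE 4.03. No other scale is named for the two exempted events. The section defines them instead. Hypoglycemia is an adverse event if it causes unconsciousness or a seizure, or if altered consciousness makes help from others necessary. Hyperglycemia is one if it leads to DKA. The section still asks for severity or grade to be recorded in the source documents.
- **General adverse event definition (11.2.1):** covers anything new or worse than at baseline in severity or frequency, and abnormal laboratory results.
- **Metabolic assessments (10.1.3):** include "Insulin use and home blood glucose measurements". Section 10.1 refers the reader to Attachment 1 for the schedule. Attachment 1 has no row for either item.

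**The concern.** In this population, DKA and severe hypoglycemia are the acute events most closely tied to the underlying disease. With a drug new to T1D and no control arm, one would want such an admission after the infusion to be classified by a fixed rule. As written, an unplanned admission for pneumonia is serious because the subject was admitted. An unplanned admission for DKA is not serious on that ground and depends on a further judgment about danger or importance. Two comparable DKA admissions could be classified differently, and the SAE listing could understate glycemic harm.

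Below the level of an admission, the plan names two measures that would show a change in glycemic control after dosing, but gives no visit at which they are collected. It also gives two different answers to whether such a change is an adverse event.

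**Working it through.** The plan states no figure on this point, so the check is mainly a comparison of passages.

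**1. Scope of the exception.** The wording in 11.2.4 turns on the reason for admission (glycemic control). Whether the admission was planned plays no part.

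| Event after infusion | Adverse event? | Serious by the hospitalization criterion? |
|---|---|---|
| Unplanned admission, non-glycemic cause | Yes | Yes |
| Planned admission to adjust glycemic control | Depends on 11.2.1 and 11.3 | No |
| Unplanned admission for DKA | Yes (11.3) | No |
| Unplanned admission for hypoglycemia with a seizure | Yes (11.3) | No |

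The last two rows are the problem. They receive the same treatment as a planned admission.

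**2. Routes to seriousness that remain.** For a non-fatal event these are life-threatening, incapacity and important medical event. The first is itself a judgment: "A life-threatening event is any adverse therapy experience that, in the view of the investigator, places the participant at immediate risk of death". The important-medical-event route also rests on medical judgment, although its footnote leans toward calling such events serious.

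**3. What classification changes.** Under 11.4.1 an SAE goes to the funder within 24 hours if it is also unexpected and possibly or probably drug-related, and reporting runs for 30 days after the dose. The last visit is on Day 84 with a window of 7 days, so up to Day 84 + 7 = 91. Being classed as serious is therefore necessary for the 11.4.1 report and not sufficient. Section 11.3.1 also sets explicit rules for following unresolved SAEs past the end of study. For other adverse events, 11.3 has a general duty to observe until they resolve or stabilize.

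**4. Two thresholds for an adverse event.** Take a subject whose hypoglycemia becomes more frequent after the infusion but never requires help. Under 11.2.1 this is an adverse event, because frequency has increased from baseline. Under 11.3 it is not a hypoglycemic adverse event. The plan does not say which section governs.

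**5. Severity.** Section 11.3 removes CTCAE for glycemic events, then requires severity or grade. No basis is given for these events.

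**6. Schedule.** General Assessments, which include adverse event review and concomitant medications, are marked at all six visits. Insulin is not named among the concomitant medications. The chemistry panel is also marked at every visit, but the analytes listed in 10.1.2 do not include glucose. Nothing in Attachment 1 therefore secures insulin-use or home-glucose data after dosing.

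**7. How many admissions could be affected.** The documents give no admission rate. Assume a probability p per subject over follow-up, and N = 10 (12.2). Expected number = 10p; chance of at least one = 1 − (1 − p)^10.

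| Assumed p | Expected admissions | Chance of at least one |
|---|---|---|
| 1% | 0.1 | 9.6% |
| 5% | 0.5 | 40.1% |
| 10% | 1.0 | 65.1% |

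Over this range, zero or one affected admission is the likely outcome.

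**The case against.** The strongest reply is that the plan captures these events. Section 11.3 names DKA and severe hypoglycemia as adverse events. All adverse events are collected regardless of cause from consent to the last procedure, with review at every visit. The safety endpoint in the synopsis is adverse events, with no SAE count. This stands. A reader might infer that the trial could miss a post-infusion DKA admission altogether, and the documents do not support that.

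A second reply is that every seriousness criterion is already subject to the sponsor investigator's view, and that the exception is a deliberate way to avoid reporting background disease. The first part is correct on the text. Even so, admission is an observable fact, whereas the remaining routes for a non-fatal event call for a clinical appraisal. The second part explains excluding planned admissions. It is weaker for unplanned ones in a trial of 10 subjects, where the reporting burden saved is slight.

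Three further inferences should be resisted:
- HbA1c and the mixed-meal test appear at Visit 1 only. This is not a defect. The meal test serves eligibility (7.2), HbA1c is a possible correlate of p-STAT3 modulation (12.1), and there is no metabolic endpoint.
- Glycemic events are absent from the special-interest list. Section 11.2.3 confines that list to signals already in the prescribing information.
- One unclassified admission would change the SAE result from 0/10 to 1/10. That is true of any single event of any kind, and Section 12 plans no estimate of an SAE rate.

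**Conclusion.** The point holds in a limited form. An unplanned glycemic admission after the infusion is recorded as an adverse event but is not automatically serious, so it can be under-classified against a safety objective set in T1D. Separately, insulin use and home glucose are listed without a schedule, 11.2.1 and 11.3 disagree on when glycemic worsening is an adverse event, and severity has no stated basis for glycemic events.

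The size is modest: probably zero or one admission, on the assumed probabilities of 1% to 10% per subject. For an admission to go unclassified as serious, the investigator would also have to judge that no other criterion applies. A reader might infer that removing the exception guarantees rapid reporting to the funder. It does not, because the other conditions in 11.4.1 still apply. The primary endpoint and the sample size are unaffected.

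**What to change.** 1. In 11.2.4, limit the exception to planned or elective admissions, so that an unplanned admission for a glycemic event is classified as an SAE.
2. In Attachment 1, add a row for insulin use and home blood glucose at the existing visits, to match 10.1.3.
3. Reconcile 11.2.1 with 11.3, stating which definition governs glycemic worsening that falls short of the 11.3 events.
4. In 11.3, state the basis on which severity or grade is assigned to glycemic events.

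These changes affect classification and data capture only and set no clinical rule. The cost is a wording amendment, one case-report item at visits that already take place, and possibly one SAE report for an admission that proves to be disease-related.

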11.2.5. Special Reporting Situations

Adverse events of interest for a Janssen medicinal product that require expedited reporting and/or safety valuation include, but are not limited to:

- Drug exposure during pregnancy (maternal and paternal);
- Overdose of a Janssen medicinal product;
- Exposure to a Janssen medicinal product from breastfeeding;
- Suspected abuse/misuse of a Janssen medicinal product;
- Inadvertent or accidental exposure to a Janssen medicinal product;
- Medication error involving a Janssen medicinal product (with or without patient exposure to the Janssen medicinal product, e.g., name confusion);
- Suspected transmission of any infectious agent via administration of a medicinal product;
- Any failure of expected pharmacological action (i.e., lack of effect) of a Janssen medicinal product
- Unexpected therapeutic or clinical benefit from use of a Janssen medicinal product

These safety events may not meet the definition of an adverse event; however, from a Janssen Research & Development perspective, they are treated in the same manner as adverse events.

Confidential Page 17 of 28

Any special situation that meets the criteria of a serious adverse event should be recorded on a Serious Adverse Event Report Form and be reported to the COMPANY within 24 hours of becoming aware of the event.

11.2.6. Product Quality Complaint (PQC)

A product quality compliant is defined as any suspicion of a product defect related to a potential quality issue during manufacturing, packaging, release testing, stability monitoring, dose preparation, storage or distribution of the product, or delivery system. Not all PQCs involve a subject. Lot and batch numbers are of high significance and need to be collected whenever available.

Examples of PQC include but not limited to:

- Functional Problem: e.g., altered delivery rate in a controlled release product
- Physical Defect: e.g. abnormal odor, broken or crushed tablets/capsules
- Potential Dosing Device Malfunction: e.g., auto injector button not working, needle detaching from syringe
- Suspected Contamination
- Suspected Counterfeit

11.3. Safety assessments and Collection of Safety Data

This is an exploratory study designed to assess the effects of a single dose of Siltuximab on a select set of immune parameters. All adverse events, regardless of causality, special reporting situations, and product quality complaints will be collected from the time a subject has signed and dated an Informed Consent Form (ICF) until completion of the subject's last study-related procedure (which may include contact for follow-up safety).

The Investigator(s) will treat participants with adverse events appropriately and observe them at suitable intervals until the events resolve or stabilize. Adverse events may be discovered through:

- observation of the participant;
- questioning the participant;
- unsolicited complaints by the participant.

All serious adverse events, adverse events of special interest, product quality complaints, and special situations including pregnancies, whether serious or non-serious, related or not related, following exposure to Siltuximab will be documented by the Sponsor Investigator (or sub-Investigators) and recorded in subject's source documents. Events will be assessed and reported consistent with the ICH Guideline for Good Clinical Practice, 21 CFR 312.32 for expedited safety reporting, per the guidance of the DHHS Office for Human Research Protections (OHRP), and according to any reporting requirements outlined in this protocol.

Confidential Page 18 of 28

Adverse events with the exception of hypoglycemia or hyperglycemia will be graded per the National Cancer Institute's Common Terminology Criteria for Adverse Events Version 4.03 (published May 28, 2009). An adverse hypoglycemic event is defined as one resulting in loss of consciousness, seizure, or requiring assistance of others due to altered state of consciousness. An adverse hyperglycemic event is one resulting in diabetic ketoacidosis (DKA).

Duration (start and stop dates and times), severity/grade, outcome, treatment and relationship to study drug (not, unlikely, possibly, probably, or definitely related) will be recorded on source documents. The batch and lot number of the product will be recorded for all patients, including dose and date of infusion.

11.3.1.SAEs and Special Reporting Situations

All serious adverse events that have not resolved by the end of the study, or that have not resolved upon discontinuation of the subject's participation in the study, must be followed until any of the following occurs:

- The event resolves;
- The event stabilizes;
- The event returns to baseline, if a baseline value/status is available;
- The event can be attributed to agents other than the study drug or to factors unrelated to study conduct; or

It becomes unlikely that any additional information can be obtained (subject or health care practitioner refusal to provide additional information, lost to follow-up after demonstration of due diligence with follow-up efforts.

11.4. Procedures for Reporting to Janssen Research & Development

The Sponsor Investigator will provide safety information to Janssen Research & Development on adverse events, special situations including pregnancies and product quality complaints as defined within this section.

11.4.1.Serious Adverse Events

Serious adverse events that are unexpected and possibly or probably drug related as defined in Section 11.2.4 will be reported to Janssen Research & Development using FDA Form MedWatch 3500A within 24 hours of becoming aware of the event. Serious adverse events, with the exception of pregnancies, will be reported for 30 days after the last dose of study drug.

All follow-up information for serious adverse events that are not resolved at the end of the study or by the time of patient withdrawal must be reported directly by the Sponsor Investigator, within 24 hours of becoming aware, to Janssen Research & Development.

All available clinical information relevant to the evaluation of a related SAE or special situation is required. The Sponsor Investigator is responsible for ensuring that these cases are complete and if not are promptly followed-up. A safety report is not considered complete until all clinical details needed to interpret the case are received. Reporting of follow-up information should follow the same time line as initial reports and contain the elements summarized in section 11.2.5.

11.4.2.. Adverse Events of Special Interest

Adverse events of special interest (≥ Grade 2), as defined in Section 11.2.2, will be reported to Janssen Research & Development on a quarterly basis unless they are serious adverse events. Serious adverse events will be reported within 24 hours of learning of the event.

11.4.3.Pregnancies

Any subject who becomes pregnant during the study must be promptly withdrawn from the study and discontinue further participation.

Pregnancies in female participants or partners of male participants will be reported to Janssen Research and Development within 24 hours of learning of the event using the FDA MedWatch 3500 A form. Follow-up information regarding the outcome of the pregnancy and any postnatal sequelae in the infant will be required. Depending on local legislation this may require prior consent of the partner of the male participant.

Any abnormal pregnancy outcomes (e.g., spontaneous abortions, fetal demise, stillbirths, and congenital anomalies) will be reported to Janssen as an adverse event. Safety information to be included in each safety report is summarized in section 11.2.5.

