9.3. Study Medication Accountability

Individual doses of formulated Siltuximab will be prepared for intravenous administration by VMMC Investigational Drug Services. A drug administration log will be kept current for each participant and will contain the identification of each participant and the date and quantity of drug dispensed. All remaining unused investigational product will be destroyed locally.

9.4.Dosing

Siltuximab will be administered at a dose of 11 mg/kg as a single intravenous infusion. Dosing will be according to the individual's weight during the screening visit and the value will be rounded up by excess to the next half kilogram; i.e. 45.6 kg weight will be rounded up to 46 kg.

The Siltuximab lyophilized powder will be reconstituted according to the manufacturer's instructions (SYLVANT PACKAGE INSERT). Briefly, Siltuximab will be dissolved under aseptic conditions to a concentration of 20 mg/mL Dextrose 5% in Water. The lyophilized powder should dissolve in less than

60 minutes. Once reconstituted, and prior to further dilution, the vials must be inspected for

Confidential Page 12 of 28

particulates and discoloration. Vials containing particulates or solution discoloration are discarded. The constituted product can be kept for no more than two hours prior to addition into an infusion bag. The reconstituted product is subsequently added to a 250 mL infusion bag containing 250 mL sterile Dextrose 5% in Water.

Siltuximab will be administered intravenously over approximately 60 minutes. Subjects will be observed in the clinic for approximately 15 minutes after the end of the infusion. Vital signs (blood pressure and pulse) will be recorded within 10 minutes before, 15 minutes during, at the end, and within approximately 15 minutes after completion of the infusion. The infusion should be completed within 4 hours of the dilution of the reconstituted solution to the infusion bag.

10.STUDY PROCEDURES AND GUIDELINES

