10.1. Clinical Assessments

A schedule of procedures is provided in Attachment 1. Descriptions of all assessments are described in subsequent sections.

10.1.1.General Assessments

- Informed consent: written informed consent will be obtained from the participant before any study assessments or procedures are performed;
- Eligibility criteria: eligibility for study participation will be assessed during the screening period;
- Medical History: Relevant medical history, including history of current and previous disease, and review of systems will be obtained. Adverse events will be assessed. A directed physical exam-will be conducted as indicated by medical history;
- Concomitant medications: concomitant medications and their indications will be recorded;
- Vital Signs: Body temperature, blood pressure, pulse and respirations will be measured at Screening (Visit 1) and Baseline (Visit 2).

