ATTACHMENT 1. Schedule of Events

Table 1. Study Procedures						
Visit Number	1	2	3	4	5	6
Time Point (Day)	-14	0	1.	14 ^b	28 ^b	84 ^b
Visit Window (Day)	+/- 7	-	-	+/- 3	+/- 3	+/- 7
General Assessments	Х	Х	Х	Х	х	Х
Vital Signs	Х	Х	Х			
Islet Autoantibodies	Х					
MMTT ^a	Х					
HbA1c	Х					
HIV, HBV, HCV serology	Х					
QuantiFERON TB test	Х					
EBV, CMV Serology	Х					
EBV, CMV viral load	Х					
Urine Pregnancy Test	Х	Х				
Comprehensive chemistry panel	Х	Х	Х	Х	Х	Х
Lipid Panel	Х	Х	Х	Х	Х	Х
C-reactive Protein	Х	Х	Х	Х	Х	Х
Direct bilirubin	Х	Х	Х	х	Х	Х
Erythrocyte sedimentation rate	Х	Х	Х	Х	Х	Х
CBC	Х	Х	Х	х	Х	Х
HLA Typing and SNP Analysis	Х					
Mechanistic Assays	Х	Х	Х	Х	Х	Х
Pharmacokinetic Samples	Х	Х	Х	Х	Х	Х

^a if not performed within 60 days of study screening visit

^b blood draw Visits 4-6 may be conducted remotely

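### Section 11.4.3 ends participation for a pregnancy found after the only infusion: no dose is avoided, but scheduled safety assessments, labs and drug-level samples stop

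*Combined protocol and SAP*

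**What the plan says.** On pregnancy, Section 11.4.3 says: "Any subject who becomes pregnant during the study must be promptly withdrawn from the study and discontinue further participation". The sentence does not distinguish pregnancies found before the infusion from those found after it.

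On dosing, Section 9.4 says: "Siltuximab will be administered at a dose of 11 mg/kg as a single intravenous infusion". In Attachment 1 the pre-dose pregnancy test falls at Visit 2 (Day 0), and Visits 3 to 6 follow on Days 1, 14, 28 and 84.

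On scheduled observation, Attachment 1 marks "General Assessments" at all six visits, and Section 10.1.1 says that within these "Adverse events will be assessed". The chemistry, lipid, CRP, direct bilirubin, ESR and CBC rows are also marked at every visit, as are the mechanistic and PK rows.

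On follow-up of a pregnancy, Section 11.4.3 adds: "Follow-up information regarding the outcome of the pregnancy and any postnatal sequelae in the infant will be required". It continues: "Any abnormal pregnancy outcomes (e.g., spontaneous abortions, fetal demise, stillbirths, and congenital anomalies) will be reported to Janssen as an adverse event". Section 11.2.5 lists exposure in pregnancy as a special reporting situation, and Section 11.4.1 says: "All available clinical information relevant to the evaluation of a related SAE or special situation is required".

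**The concern.** In a repeat-dose trial, withdrawal for pregnancy prevents further exposure. Here nothing remains to be given once the infusion is complete, so a rule written for safety has only one effect after Day 0: it ends scheduled observation of someone already exposed.

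Section 14.2 says that effects on pregnant women and unborn babies have not been studied. A woman exposed shortly before or early in pregnancy is therefore one whose routine labs, adverse-event visits and drug levels are worth having. Section 14.5 allows a subject without evaluable mechanistic data to be replaced. A replacement restores the count of evaluable subjects but does not recover this woman's own safety and drug-level record.

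**Working it through.** The point rests mainly on reading the sections side by side. The only arithmetic is a count from Attachment 1.

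**Step 1: exposure avoided.** Planned infusions per subject: 1 (Section 9.4). Given by the end of Visit 2: 1. Remaining: 1 − 1 = 0.

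**Step 2: pregnancy found before the infusion.** Inclusion criterion 4 requires a negative test at screening and before dosing. Exclusion criterion 10 bars pregnant women, and Section 10.1.2 and Attachment 1 schedule the tests. Here the withdrawal sentence adds no protection that eligibility does not already give.

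**Step 3: what stops after the infusion.** Nine rows of Attachment 1 are marked at every visit:
- seven safety rows: General Assessments, chemistry, lipids, CRP, direct bilirubin, ESR, CBC;
- one PK row;
- one mechanistic row.

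Entries forgone = remaining visits × rows:

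| Withdrawn after | Visits left | Safety | PK | Mechanistic | Total |
|---|---|---|---|---|---|
| Visit 3 (Day 1) | 3 | 3 × 7 = 21 | 3 | 3 | 27 |
| Visit 4 (Day 14) | 2 | 2 × 7 = 14 | 2 | 2 | 18 |
| Visit 5 (Day 28) | 1 | 1 × 7 = 7 | 1 | 1 | 9 |

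These are schedule entries. Many come from the same blood draw, so the number of visits is the better measure of size: three, two or one. No pregnancy test is scheduled after Day 0, so the time of recognition cannot be predicted from the plan.

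**Step 4: what continues.**

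| Item | Source | After withdrawal |
|---|---|---|
| Pregnancy outcome and infant sequelae | 11.4.3 | Continues |
| Abnormal outcomes reported as adverse events | 11.4.3 | Continues |
| Unresolved serious adverse events | 11.3.1 | Continues |
| Known adverse events, until resolved or stable | 11.3 | Continues |
| General Assessments at Days 14, 28, 84 | Attachment 1 | Stops |
| Safety labs at Days 14, 28, 84 | Attachment 1 | Stops |
| PK and mechanistic samples at Days 14, 28, 84 | Attachment 1 | Stops |

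The Section 11.4.1 requirement concerns information that is available. It does not schedule any lab or sample. Section 11.3 collects adverse events up to the last study-related procedure, possibly including a safety contact. Whether new events would still be sought after withdrawal is therefore not settled by the text.

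**Step 5: a fetal-safety reason to stop.** After Visit 3 the schedule holds only General Assessments and blood tests, and the mixed-meal test is a screening procedure. Nothing listed for Days 14 to 84 explains stopping on fetal-safety grounds.

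**The case against.** The strongest reply is that the plan already follows the outcomes that matter most. The pregnancy and the infant are followed, known adverse events are observed and unresolved serious ones are pursued. What is lost is routine protocol blood work and research samples. This stands, and it limits the point. A reader might infer that the plan abandons an exposed woman; Sections 11.3, 11.3.1 and 11.4.3 show that it does not.

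The rule is also defensible for the endpoint. Pregnancy is excluded at entry, and Section 8.1 restricts vaccines because they may affect the outcome. Leaving out a Week 12 sample taken in pregnancy and replacing the subject is a coherent choice. This stands too, but it is a reason to handle her mechanistic sample separately. It is not a reason to stop her safety labs.

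A reader might further infer that the rule weakens the primary test. The documents do not support that. Section 12.2 says 9 subjects are needed and plans 10 with evaluable data, and Section 14.5 permits replacement. A power figure also needs a within-subject correlation r, which the plan does not give. Take a difference of 0.5 × 3.2 = 1.6, an SD of the difference of 1.3 × √(2(1 − r)), and the exact two-sided paired t-test at 0.05. The plan's 9 is then reproduced at r = 0.35 to 0.40. Going from 10 to 9 pairs would take power from 83.3% to 78.0% at r = 0.3, from 93.2% to 89.7% at r = 0.5, and from 99.3% to 98.5% at r = 0.7. Those losses require both a pregnancy and no replacement. Retaining her would not reliably recover them, because a sample taken in pregnancy may be confounded.

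Finally, the event is uncommon: there are 10 subjects of both sexes, with effective birth control required of women of child-bearing potential. That is conceded.

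**Conclusion.** The point holds in limited form. After the single infusion, the withdrawal rule prevents no exposure and ends up to three scheduled visits of safety assessments, labs and PK sampling in a woman exposed to a drug not studied in pregnancy. If the pregnancy is recognised only after Day 28, the loss is one visit.

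Severity is low. There is no effect unless a pregnancy occurs, and the documents give no probability for that. The conclusion assumes that ending participation means the remaining Attachment 1 visits are not held; the text offers no exception. It is a cheap improvement to safety follow-up and does not identify a flaw in the primary analysis.

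**What to change.** Amend Section 11.4.3 as follows.

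1. Pregnancy found before infusion: do not dose, as the eligibility criteria already require.
2. Pregnancy found after infusion: do not withdraw the subject for that reason. Continue the scheduled General Assessments and safety labs through Day 84, alongside the existing pregnancy and infant follow-up.
3. If she agrees, continue the remaining PK and research draws. Refusing these must not end her safety follow-up.
4. Flag every sample taken during pregnancy. Keep flagged samples out of the primary paired t-test unless the plan states otherwise before analysis; a sensitivity result may include them.
5. Let replacement under Section 14.5 apply if her Week 12 sample is not evaluable.

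The cost is a short protocol and consent amendment with IRB approval (Section 14.3). Compared with the present rule, a pregnant subject would have up to three more blood-draw visits, which Attachment 1 allows to be remote. Section 14.1 offers her no direct benefit beyond closer monitoring. Replacement may still mean infusing one more person, so the change does not remove that consequence.
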